10.4.2 Serious adverse events waived from expedited regulatory reporting to regulatory authorities

Disease progression is anticipated for the disease being treated (ie, IPF) and will be considered expected for the purpose of regulatory reporting. Conversely, an event more severe than anticipated usual disease progression is to be considered unexpected.

If a serious and unexpected adverse event occurs for which there is evidence suggesting a causal relationship between the drug and the event [Suspected Unexpected Serious Adverse Reaction (SUSAR)], the event must be reported, even if it is a component of the study endpoint.

10.4.3 General guidelines for reporting adverse events

- All AEs, regardless of seriousness or relationship to IMP/NIMP, spanning from the signature of the informed consent form until the end of the study as defined by the protocol for that patient, are to be recorded on the corresponding page(s) or screen(s) of the e-CRF.
- Whenever possible, diagnosis or single syndrome should be reported instead of symptoms. Only one diagnosis (symptom if relevant) to be MedDRA coded should be reported per AE report form. The Investigator should specify the date of onset, intensity, action taken with respect to IMP, corrective treatment/therapy given, additional investigations performed, outcome, and his/her opinion as to whether there is a reasonable possibility that the AE was caused by the IMP or by the study procedure(s).

- The Investigator should take appropriate measures to follow all AEs until clinical recovery is complete and laboratory results have returned to normal, or until progression has been stabilized, in order to ensure the safety of the patients, or until death. This may imply that observations will continue beyond the last planned visit per protocol, and that additional investigations may be requested by the monitoring team up to as noticed by the Sponsor.
- When treatment is prematurely discontinued, the patient's observations will continue until the end of the study as defined by the protocol for that patient.
- Laboratory, vital signs or ECG abnormalities are to be recorded as AEs only if:
 - Symptomatic and/or
 - Requiring either corrective treatment or consultation, and/or
 - Leading to IMP discontinuation or modification of dosing, and/or
 - Fulfilling a seriousness criterion, and/or
 - Defined as an AESI
- Instructions for AE reporting are summarized in [TABLE 2](#).

10.4.4 Instructions for reporting serious adverse events

In the case of occurrence of a SAE, the Investigator must immediately:

- ENTER (within 24 hours) the information related to the SAE in the appropriate screens of the e-CRF; the system will automatically send a notification to the monitoring team after approval of the Investigator within the e-CRF or after a standard delay.
- SEND (preferably by fax or e-mail) a photocopy of all examinations carried out and the dates on which these examinations were performed, to the representative of the monitoring team whose name, fax number, and email address appear on the clinical trial protocol. Care should be taken to ensure that the patient's identity is protected and the patient's identifiers in the clinical trial are properly mentioned on any copy of a source document provided to the Sponsor. For laboratory results, include the laboratory normal ranges.
- All further data updates should be recorded in the e-CRF as appropriate, and further documentation as well as additional information (for laboratory data, concomitant medications, patient status, etc) should be sent (by fax or e-mail) to the monitoring team within 24 hours of knowledge of the SAE. In addition, every effort should be made to further document any SAE that is fatal or life threatening within a week (7 days) of the initial notification.
- A back-up plan (using a paper CRF process) is available and should be used when the e-CRF system does not work.

Any SAE brought to the attention of the Investigator at any time after the end of the study for the patient and considered by him/her to be caused by the IMP with a reasonable possibility, should be reported to the monitoring team.

10.4.5 Guidelines for reporting adverse events of special interest

For AESIs, the Sponsor must be informed immediately (i.e. within 24 hours), as per SAE notification guidelines described in [Section 10.4.4](#), even if not fulfilling a seriousness criterion, using the corresponding pages of the CRF (to be sent) or screens in the e-CRF.

Instructions for AE reporting are summarized in [TABLE 2](#).

10.4.6 Guidelines for management of specific laboratory abnormalities

Decision trees for the management of certain laboratory abnormalities by Sanofi are provided in [APPENDIX F](#).

The following laboratory abnormalities should be monitored, documented, and managed according to the related flow chart in protocol appendices.

- Neutropenia
- Thrombocytopenia
- Increase in ALT
- Acute renal insufficiency
- Suspicion of rhabdomyolysis

NOTE: However, if a seriousness criterion is met, the Sponsor is informed immediately (ie, within 1 working day) using the corresponding screens in the eCRF, following the same process as described for the SAEs.

Table 2 - Summary of adverse event reporting instructions

Event category	Reporting timeframe	Specific events in this category	Case Report Form completion		
			AE form	Safety Complementary Form	Other specific forms
Adverse Event (non-SAE, non-AESI)	Routine	Any AE that is not SAE or AESI	Yes	No	No
Serious Adverse Event (non-AESI or AESI)	Expedited (within 24 hours)	Any AE meeting seriousness criterion per Section 10.4.1.2	Yes	Yes	No
Adverse Event of Special Interest	Expedited (within 24 hours)	Pregnancy	Yes	Yes	No
		Symptomatic overdose	Yes	Yes	No
		ALT \geq 3 ULN (if baseline ALT<ULN) and ALT \geq 2 x baseline (if baseline ALT \geq ULN)	Yes	Yes	Yes
			Yes	Yes	Yes
		Anaphylactic reactions or acute allergic reactions	Yes	Yes	Yes
		Severe injection site reactions	Yes	Yes	Yes
		TB or initiation of medications for suspected TB	Yes	Yes	Yes
Acute renal failure	Yes	Yes	No		

10.5 OBLIGATIONS OF THE SPONSOR

During the course of the study, the Sponsor will report in an expedited manner:

- All SAEs that are both unexpected and at least reasonably related to the IMP (SUSAR), to the regulatory authorities, IECs/IRBs as appropriate and to the Investigators.
- All SAEs that are expected and at least reasonably related to the IMPs to the regulatory authorities, according to local regulations.

In this study, some AEs are considered related to the underlying condition and thus will not be considered unexpected, please refer to the Investigator's Brochure (IB).

Any other AE not listed as an expected event in the Investigator's Brochure or in this protocol will be considered unexpected.

For regulatory purposes, the treatment code will be unblinded at Sponsor Pharmacovigilance department level for reporting to the Health Authorities of any suspected unexpected adverse drug reaction (SUSAR) and reasonably associated with the use of the IMP according to either the judgment of the Investigator and/or the Sponsor. Apart from Sponsor Pharmacovigilance department, within the company and associated organizations, the results of this unblinding will remained undisclosed.

The Sponsor will report all safety observations made during the conduct of the trial in the clinical study report and in the development safety update report.

10.6 SAFETY INSTRUCTIONS

10.6.1

[REDACTED]

If neurological signs or symptoms are identified, the patient should be addressed to a neurologist specialized in inflammatory processes for consultation.

| [REDACTED]

| [REDACTED]

[REDACTED]

| [REDACTED]

10.6.2 Tolerability at the IMP injection

10.6.2.1 Local injection site reactions

Local injection site reactions that are considered as non-allergic events should be further characterized and evaluated with the assessment of the severity grading of related symptoms such as corresponding for pain, tenderness, erythema/redness, swelling, itching or other (See [APPENDIX E](#)). Special e-CRF screens will need to be completed. If such an AE was to occur, then do not report the individual components of the reaction but rather the term “local injection site reaction”, the individual components being described in the specific e-CRF screen.

10.6.3 Systemic allergy reaction

10.6.3.1 Anaphylaxis

Allergic reaction is a potential risk associated with the administration of most therapeutic monoclonal antibodies.

Acute allergic reactions may be defined as allergic reaction-mediated signs and symptoms experienced by patients during or shortly after the pharmacologic or biologic agent is given. These reactions may present in a variety of ways, including dizziness, headache, anxiety, dyspnea, hypotension, tachycardia, pruritus, rash, urticarial/angioedema, flushing, nausea, or vomiting. Anaphylaxis may represent the most severe form of infusion reaction, but these events may also occur via other immune-mediated mechanisms (e.g. cytokine-mediated). Allergic reactions may begin within few hours and persist up to 24 hours post dosing. Refer to [APPENDIX D](#) “Definition of anaphylaxis”, which describes the clinical criteria for the diagnosis of anaphylaxis.

Patients should be monitored by site personnel or visiting nurse (if injection performed at patient’s home) for at least 30 minutes after each administration of investigational product for any signs or symptoms of a hypersensitivity reaction.

[For Czech Republic only, per local requirement: Patients should be monitored at the study site by site personnel for at least 2 hours after the first administration of IMP and at least 1 hour after the next 5 administrations for any signs or symptoms of a hypersensitivity reaction. For the subsequent IMP administrations, patients should be monitored by site personnel or visiting nurse (if injection performed at patient’s home) for at least 30 minutes after each administration of IMP.]

Patients should be treated symptomatically if any AEs are observed. General Allergic Reaction and/or Local Injection Site Reaction Complementary Form will have to be completed.

Sometimes transient injection site reactions, irritant in nature, may occur, requiring no intervention and being of dubious significance. These reactions would not be considered to be allergic reactions, and should only be recorded on the Local Injection Site Reaction Complementary Form.

The IMP should be immediately interrupted (temporarily discontinued) if there is a suspicion of an allergic event related to IMP. Refer to [Section 10.4.1.3](#) for hypersensitivity reactions to be reported as AESIs, and to [Section 10.3](#) for hypersensitivity reactions requiring permanent treatment discontinuation.

10.6.3.2 Allergic adverse event with cutaneous involvement

Adverse events with cutaneous involvement which are obviously of allergic origin or injection site reactions which progress/expand/worsen/etc. should be evaluated by a dermatologist as soon as possible, and preferably within one week of the site first becoming aware of the event.

The Investigator should evaluate the patient for possible etiologies (new medications, etc.) and extracutaneous symptoms and signs. An unscheduled Central Laboratory assessment for hematology, chemistry, liver panel, PK, and ADA should be obtained. If it is possible, the site will take pictures of the skin lesions in order to provide the patient with them for the dermatologist's visit. If the photos are obtained, then copies should be kept as source documents which may later be collected by the sponsor. The Investigator will provide a summary of the patient's case, reason for consultation, and information being requested to the consulting dermatologist.

A full consultation report should be sent by the dermatologist to the Investigator. The full report should contain, at a minimum, the following information; a detailed description of the skin reaction (such as the morphology [lesion type], shape of individual lesions, arrangement of multiple lesions [e.g. scattered, grouped, linear], distribution, color, consistency, presence of pruritus or pain, and other clinical signs) and, in case a skin biopsy was done based on the dermatologist's or Investigator's medical judgment, the results of this investigation (including histopathology and immunofluorescence), with, if applicable, a specific diagnosis of the AE to be reported in the verbatim. The Investigator will email or fax the full report and the corrected AE form if necessary, to the Monitoring Team Representative within 24 hours.

10.7 ADVERSE EVENTS MONITORING

All events will be managed and reported in compliance with all applicable regulations, and included in the final clinical study report.

11 STATISTICAL CONSIDERATIONS

11.1 DETERMINATION OF SAMPLE SIZE

Approximately 300 patients will be randomized in this study, 100 per treatment group. Based on the enrollment in prior studies of this population approximately half of the patients are expected to be older than 65.

The sample size calculations are based on the primary efficacy variable of % predicted FVC change from baseline to week 52, with the following assumptions:

- A common standard deviation of 12% is assumed based on the data from previous trials (26)
- A 5 % mean difference between each dose and placebo in change from baseline in % predicted FVC
- A 2-sided 5% significance level with 80% power

Ninety two (92) patients per treatment group will yield 80% power to detect a 5 percentage point difference between the treatment groups and placebo. Additional patients will be randomized in each regimen to allow for dropouts; therefore, approximately 100 patients will be randomized into each treatment group, for a total sample size of approximately 300 patients for the study.

As a rank-based method will be used for analysis the actual power may differ from these calculations, however, calculations based on the ASCEND study (28), which used the same analysis method and endpoint confirm that the planned analysis should have at least 80% power. No adjustment is made for multiplicity since a hierarchical testing procedure is proposed.

Calculations were made using nQuery Advisor 7.0

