	
 • Tolerability at the investigational medicinal product (IMP) injection site: 
 - Erythema (diameter and graded severity) - Swelling/induration/edema (diameter and graded severity) - Pain assessment 
Immunogenicity
 
Testing for anti-drug antibodies (ADA)
 
Biomarker quantification
 
 • Blood biomarkers which may predict response to drug, disease progression and provide evidence of drug action will be collected including but not limited to inter-cellular adhesion molecule 1 (ICAM1), TARC, periostin and HE4 • Archived blood samples will be performed for future assay of protein and mRNA biomarkers related to the diagnosis, progression, or therapeutic responsiveness of IPF 
Pharmacokinetics
 
Population PK analysis of plasma SAR156597 concentrations to predict PK parameters at steady state (Cmax, tmax, AUC0-168 &/or AUC0-336) and time to reach steady state.

ASSESSMENT SCHEDULE
	
The study will comprise 10 on-site visits AND 9 phone calls:
 
 • Visits: 
 - V1 screening visit between D -28 and Day -1 - V2 baseline visit at D1 (first dosing) - during the treatment period*: 
 - visit every 2 weeks from V2 to V5 - every 6 weeks from V5 to V6 - every 12 weeks from V6 to V8 - every 16 weeks from V8 to V9 (Week 52; last dosing) - V10 follow-up visit at Week 64 - A time window of ± 2 days will be allowed for each visit • Phone calls: 
 - For safety considerations at Weeks 8, 16, 20, 28, 32, 40, 44, 48 during the treatment period and at Week 58 during the follow-up period. 
*IMP administration being every week.

STATISTICAL CONSIDERATIONS
	
Sample size determination:
 
Based on prior clinical trial experience in IPF patients, it is estimated that the standard deviation (SD) of the absolute change in % predicted FVC at 52 weeks is approximately 12%. For the primary efficacy parameter of absolute change in % predicted FVC, 92 patients per treatment group will yield 80% power to detect a 5 percentage point difference between the treatment groups and placebo. Additional patients will be randomized in each regimen to allow for dropouts; therefore, approximately 100 patients

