11.4.2.3 Multiplicity considerations

The overall type I error rate for this study is 5%. A hierarchical testing procedure will be used to control the type I error over the two doses. The qw dose group will be compared to placebo first, and only if this comparison is significant will the q2w dose group be compared to placebo.

The same procedure will be used for the disease progression endpoint if significance is achieved for both doses on the primary endpoint.

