### **1.3 DETERMINATION OF SAMPLE SIZE**

Approximately 300 patients will be randomized in this study, 100 per treatment arm. Based on the enrollment in prior studies of this population approximately half of the patients are expected to be older than 65.

The sample size calculations are based on the primary efficacy variable of % predicted FVC change from baseline to week 52, with the following assumptions:

- A common standard deviation of 12% is assumed based on the data from previous trials (26)
- A 5% mean difference between each dose and placebo in change from baseline in % predicted FVC
- A 2-sided 5% significance level with 80% power

Ninety two (92) patients per treatment arm will yield 80% power to detect a 5 percentage point difference between the treatment groups and placebo. Additional patients will be randomized in each regimen to allow for dropouts; therefore, approximately 100 patients will be randomized into each treatment arm, for a total sample size of approximately 300 patients for the study.

[figure not shown]
As a rank-based method will be used for analysis the actual power may differ from these calculations, however, calculations based on the ASCEND study (28), which used the same analysis method and endpoint confirm that the planned analysis should have at least 80% power. No adjustment is made for multiplicity since a hierarchical testing procedure is proposed.

Calculations were made using nQuery Advisor 7.0.

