    - iii. Other: Absolute change from baseline at 52 weeks in % predicted FVC values will be calculated from observed and imputed week 52 % predicted FVC values and then ranked (from  $n_{\text{stratum,death}}+n_{\text{stratum,lungtransplant}} + 1$  to  $n_{\text{stratum}}$ ).
    - iv. Standardization of ranks using the NPLUS1 option of PROC RANK on SAS with the by statement for the stratification factor (with/without Background Therapy).
  - b) Adjustment on baseline % predicted FVC covariate
    - i. The residuals from the linear regression of response ranks on baseline ranks will be calculated within each stratum of the stratification factor (with/without Background Therapy) using the following PROC GLM on SAS:

```
proc GLM data=xx;  
by stratification_factor;  
model chg_Rank=base_Rank;  
output out=residual r=resid;  
run;
```

- c) Test of treatment effect using the CMH2 option of PROC FREQ on SAS and the residuals as scores
  - i. The qw arm will be compared to placebo using a Mantel-Haenszel mean score chi-square test at a two-sided type-I error level of 5%. This test will be stratified on the stratification factor.

B) On the pool of arms SAR156597 200mg q2w and placebo:

Same steps as A except for 2c: the q2w arm will be compared to placebo using a Mantel-Haenszel mean score chi-square test at a two-sided type-I error level of 5% only if the qw arm versus placebo comparison was significant. This test will be stratified on the stratification factor.

Descriptive statistics for values and changes from baseline will be presented by treatment arm and background therapy status for each time point. The mean (SD) % predicted FVC values and the mean (SD) absolute change from baseline in % predicted FVC over time will be graphically represented by treatment arm and by background therapy status without any imputation.

A specific table will describe the following items by treatment arm and background therapy:

- The number (%) of patients with an observed week 52 value for % predicted FVC
  - The mean (SD) and median (Q1:Q3) of baseline and week 52 values of % predicted FVC for those patients
  - The mean (SD) and median (Q1:Q3) of absolute change from baseline at 52 weeks in % predicted FVC for those patients
- The number (%) of patients having a missing data due to death at week 52,
- The number (%) of patients having a missing data due to lung transplant at week 52,

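### The stated 80% power is per comparison and belongs to qw; because q2w is tested only after a significant qw result, its power on the plan's own assumptions is about 69% to 74%, and neither document says so

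*Protocol*

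**What the plan says.** The sample-size assumptions are a common SD of 12 points, a two-sided 5% level, 80% power, and the same effect for both regimens. SAP 1.3 words the effect as "A 5% mean difference between each dose and placebo in change from baseline in % predicted FVC", and Protocol 11.1 agrees. From these, Protocol 11.1 concludes: "Ninety two (92) patients per treatment group will yield 80% power to detect a 5 percentage point difference between the treatment groups and placebo". SAP 1.3 and the synopsis give the same conclusion. About 100 per group are randomized to allow for dropouts.

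Protocol 11.1 and SAP 1.3 add that the rank-based method may alter the power, but that calculations based on a cited earlier trial "confirm that the planned analysis should have at least 80% power". They do not say which comparison this covers. The next sentence in both says that multiplicity is not adjusted for because testing is hierarchical. The synopsis does not mention the hierarchy in its power statement.

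The hierarchy is set out elsewhere. Under Protocol 11.4.2.3, qw is compared with placebo first and "only if this comparison is significant will the q2w dose group be compared to placebo". SAP 2.4.4.1, step B, runs the q2w test "only if the qw arm versus placebo comparison was significant", and SAP 2.4.4.3 repeats the rule. On the key secondary endpoint, Protocol 11.4.2.3 says: "The same procedure will be used for the disease progression endpoint if significance is achieved for both doses on the primary endpoint".

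**The concern.** The power sentence speaks of the treatment groups in the plural and rests on an effect assumed for each dose, so it reads as 80% for both regimens. Under the planned sequence, q2w can be declared effective only if two tests succeed. The probability of that is below the power of either test alone.

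This matters because the primary objective covers both regimens, and Protocol 4.2.2 calls dosing every 2 weeks the desired frequency for patient convenience. A reader who takes 80% at face value puts the chance of missing a true 5-point q2w effect at 20%; on the plan's assumptions it is about 26% to 31%. The same applies to the chance that disease progression is never formally tested.

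**Working it through.** **Inputs.** Difference 5 points for each dose, SD 12, two-sided alpha 0.05, n = 92 (Protocol 11.1, SAP 1.3); 100 randomized per arm; 1:1:1 allocation (Protocol 8.4). No dropout rate is stated; 92 of 100 implies 8%.

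**1. Reproduce the stated figure.** Two-sample t test with 2n − 2 degrees of freedom and noncentrality 5 / (12 × √(2/n)).
- n = 92: 5 / (12 × 0.1474) = 2.826; power 80.3%.
- n = 91: power 79.8%, so 92 is the smallest n that reaches 80%.
- n = 100: 5 / (12 × 0.1414) = 2.946; power 83.4%.

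The 80% is therefore the power of one comparison with placebo.

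**2. Correlation of the two tests.** Both use the same placebo mean. The covariance of the two differences is 144/n and each variance is 2 × 144/n, so the correlation is 0.5. Multiplying the powers as if independent (0.8026² = 64.4% at 92) would be too pessimistic.

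**3. Probability that both tests are significant,** with both true effects at 5 points. This is the power to declare q2w effective under the sequence, and also the probability of reaching the disease-progression test.

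| Evaluable per arm | qw (one comparison) | q2w through the sequence, simulated t tests | Same, bivariate normal | q2w given qw significant |
|---|---|---|---|---|
| 92 | 80.3% | 69.1% | 69.6% | 0.691 / 0.803 = 86.1% |
| 100 | 83.4% | 73.6% | 74.0% | 0.736 / 0.834 = 88.2% |

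The simulation used 1,000,000 replicates. The shortfall against the per-comparison figure is 80.3 − 69.1 = 11.2 points at 92 and 83.4 − 73.6 = 9.8 points at 100. For scale only, sequential q2w power reaches 80% at about 114 evaluable per arm.

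**4. Sensitivity to the true qw effect** (q2w at 5 points, 92 per arm). With qw at 4 points the figure is 55%; with qw at 6 points it is 77%. It cannot exceed the per-comparison power.

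**5. Sensitivity to the test.** The planned rank ANCOVA was simulated with assumed error shapes (normal, or t with 5 df scaled to SD 12) and assumed equal death rates of 0% to 10% ranked worst. The documents give neither. Sequential q2w power ran from 41.6% (normal, 10% deaths, 92 per arm) to 82.6% (t with 5 df, no deaths, 100 per arm). The absolute level depends heavily on these assumptions, but q2w was 7 to 18 points below qw in every equal-effect run.

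**The case against.** The strongest reply is that nothing printed is arithmetically wrong. The effect is assumed per dose, 92 is the right number for it, and sizing each comparison separately is ordinary in a phase 2 proof-of-concept trial. Neither document claims 80% power to win on both doses. SAP 1.5 already describes enrolment in the past tense, so no sample-size decision is left. SAP 2.4.4.1.1 and 2.4.4.2.1 also plan q2w estimates with 90% and 95% confidence intervals. All of this stands and limits the point to disclosure. It does not close the gap between the only power figure given and the q2w test as planned.

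Three stronger readings are tempting, and the documents support none of them.

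- *The power sections conceal the hierarchy.* They do not: Protocol 11.1 and SAP 1.3 mention it immediately after the power claim. They use it only to explain the absence of a multiplicity adjustment, which is sound for type I error and says nothing about power.
- *A non-significant q2w result should be read against 69% to 74%.* If q2w is tested at all, qw has succeeded, and the relevant figure is the conditional 86% to 88%. The lower figures are the prospective chance of a q2w claim.
- *The at-least-80% statement is false for q2w.* This cannot be shown. The calculation behind it is not in the documents and its scope is not stated. One heavy-tailed rank scenario at 100 per arm gives 82.6% through the sequence. What is missing is a statement of which comparison it covers.

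**Conclusion.** The point holds as a gap in the stated power. The 80% at 92 per group is correct per comparison and is the operating power for qw. It is not the power to declare q2w effective, nor the probability of reaching the disease-progression test. Both of those are about 69% with 92 evaluable per arm and about 74% with 100.

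These figures rest on the plan's equal 5-point effects, SD 12, a shared placebo arm and a t-test approximation; the 100-per-arm figure also assumes that every randomized patient is evaluable. The level under the rank ANCOVA is uncertain, and the documents' caveat about that method is a separate matter from the sequence.

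A reader might also infer that type I error is at risk or that the trial must be enlarged. Neither follows: the fixed sequence protects the 5% level, and no power target for q2w under the sequence was set.

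**What to change.** In the synopsis, Protocol 11.1 and SAP 1.3, or at least in SAP 1.3, replace the power sentence with:

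> With 92 evaluable patients per group, each comparison with placebo has 80% power for a 5-point difference (SD 12, two-sided 5%); this is the power for qw, which is tested first. Because q2w is tested only if qw is significant, the probability of declaring q2w effective, and of reaching the disease-progression test, when both true differences are 5 points is about 69% with 92 per group and 74% with 100. If qw is significant, the conditional power for q2w is about 86% to 88%. These are t-test approximations; power under the rank ANCOVA depends on the outcome distribution.

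In Protocol 11.1 and SAP 1.3, also state which comparison the calculation from the cited trial covers. Do not add that it excludes the sequential q2w test, because that cannot be established from the documents. The 4-point and 6-point qw scenarios need not go in.

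The cost is wording in up to three places. Two of these are in the protocol, where Protocol 15 requires ethics approval of an amendment before it is implemented; if that is out of proportion, SAP 1.3 alone will serve. The downside is a less favourable stated power for q2w. Enrolment, testing order, alpha and analysis do not change.
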